### 5.2 EXCLUSION CRITERIA

An individual who meets any of the following criteria will be excluded from participation in this study:

1. Currently participating in another intervention
2. Other serious health conditions that interfere with diabetes management

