Retention & Follow-Up: Efforts will be made to maximize retention across trial assessments. These include providing study retention items (e.g., keychain flashlights, laptop decals with the study logo), sending birthday cards to trial participants, and verifying contact information, including email addresses and phone numbers, at each assessment point. As in previous studies, we will attempt to collect follow-up data in person during regularly scheduled clinic appointments. Prior to their scheduled appointment, families will be reminded of the visit and asked to come early or stay after their appointment. If families cancel or do not show for their appointments, we will email and text a unique link to the REDCap survey and continue to follow up by phone and email until surveys are completed. We will give the family the option of doing a Coremedica HemaSpot-SE HbA1c kit at home if they are unable to come into the clinic to get a point of care A1c test. If families are not responsive, we will send a paper packet with a self-addressed, stamped envelope. These methods have resulted in excellent retention rates (91-98%) in our pilot studies. We will actively work towards maintaining families' participation in data collection regardless of their engagement in the text messages so that intent-to-treat analyses may be conducted. We are conservatively planning for a ~15% attrition rate based on data from our pilot studies to protect against overestimation.

Incentives. In order to promote the completion of trial measures at all assessment points, participants will be compensated for their time at each data collection, with increasing compensation (\$20, \$25, \$30, \$30) to improve retention. In addition, participants will receive \$10 for participating in a qualitative exit interview at the 3-month data collection. Participants who complete the secondary study (interview describing their CGM use) will receive an additional \$30 gift card.

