## 7.2 PARTICIPANT DISCONTINUATION/WITHDRAWAL FROM THE STUDY

Participants are free to withdraw from participation in the study at any time upon request.

An investigator may discontinue a participant from the study for the following reasons:

- Significant study intervention non-compliance
- Lost-to-follow up; unable to contact subject
- Any event or medical condition or situation occurs such that continued collection of follow-up study data would not be in the best interest of the participant or might require an additional treatment that would confound the interpretation of the study
- The participant meets an exclusion criterion (either newly developed or not previously recognized) that precludes further study participation

The reason for participant discontinuation or withdrawal from the study will be recorded in the REDCap database. Subjects who sign the informed consent form and are randomized but do not receive the study intervention may be replaced. Subjects who sign the informed consent form, and are randomized and receive the study intervention, and subsequently withdraw, or are discontinued from the study, will not be replaced.

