## 9 STATISTICAL CONSIDERATIONS

### 9.1 STATISTICAL HYPOTHESES

- Primary Efficacy Endpoint(s):

The primary outcome is change in glycemic control (A1C). To test Aim 1, a linear mixed effects regression model will be used to estimate the effect of intervention over time on glycemic control (A1C).

- Secondary Efficacy Endpoint(s):

Our secondary outcomes are diabetes distress, coping, and diabetes management. To test Aim 2, separate linear mixed effects regression models will be used to estimate the effect of the intervention over time on diabetes distress (PAID-T), coping (RSQ), and diabetes management (P-SCI, SCI, Checks/Day). Qualitative methods will be used to code data from the secondary CGM interview study into appropriate themes that then guide analysis.

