### 9.3 STATISTICAL ANALYSES

#### 9.3.1 General Approach

Outcomes will be measured at up to four time-points per subject (baseline, 3 months, 6 months, and 12 months), so we will use time, treatment group and the interaction of treatment with time serving as the main explanatory variables. Such a model will allow us to test for any differences between treatment and control groups at 3, 6 or 12 months while accounting for baseline values. While the randomized block design should minimize confounding, we will adjust for age, sex, and race/ethnicity to improve precision. The results from the adjusted and unadjusted models will be compared with respect to their estimates of the treatment effects. We will include a random intercept to account for within-subject correlation arising from taking repeated measurements on the same subject over time. The error structure of the model is assumed to be compound symmetric, and the validity of this assumption will be examined by computing Akaike Information Criteria against other common structures. Subjects will

be included in the analysis if they have an outcome measured at baseline and at least one outcome measured at 3, 6 or 12 months.

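### Section 7.2 lets randomised teens be removed from follow-up for exclusion criteria that arise or come to light after entry, which can lose A1C values for A1C-related reasons

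*Combined protocol and SAP*

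**What the plan says.** Section 7.2 opens its list with "An investigator may discontinue a participant from the study for the following reasons", so the action is discretionary and the exit is from the study, not only from the intervention. The fourth ground is "The participant meets an exclusion criterion (either newly developed or not previously recognized) that precludes further study participation".

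Section 5.2 has two exclusion criteria: "Currently participating in another intervention" and "Other serious health conditions that interfere with diabetes management".

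The third ground in 7.2 has two parts. One covers cases where further data collection would not be in the participant's best interest. The other covers an event that might call for an extra treatment which would confound interpretation.

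Section 5.3 commits the team to maintaining families' "participation in data collection regardless of their engagement in the text messages so that intent-to-treat analyses may be conducted". The analysis set in Section 9.3.1 is restricted by this rule for each teen: "included in the analysis if they have an outcome measured at baseline and at least one outcome measured at 3, 6 or 12 months". Section 7.2 requires the reason for a discontinuation to be recorded in REDCap, but does not say whether A1C or questionnaires are collected afterwards.

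**The concern.** Exclusion criteria are normally settled at entry. Here they remain active through 12 months of follow-up, and neither is neutral with respect to the outcome. A condition that interferes with diabetes management bears on A1C by definition. Another intervention is plausibly offered more often to teens who are doing badly.

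If more such teens are removed from Education only (EDU), the control arm loses some of its worst courses and a benefit of the texting arm (TXT) is hidden. If more are removed from TXT, the benefit is inflated. Section 6.3 describes no blinding of whoever decides on removal, so unequal use of the rule is possible.

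The intent-to-treat sentence in 5.3 does not close the gap. It protects data collection only against low engagement with the texts and does not reach participants discontinued under 7.2.

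**Working it through.** **The plan's own figure.** Section 9.2 gives 200 enrolled, 15% dropout and 170 analysed: 200 × (1 − 0.15) = 170, which is reproduced. The effect sizes of Table 3 are not in the text, so the 90% power statement cannot be checked.

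**What a removal does to the data.** Under 9.3.1, a teen removed before the 3-month visit has no follow-up outcome and leaves the analysis entirely. A teen removed later keeps the earlier visits and loses the rest. The synopsis (1.1) names 3 months as the primary endpoint and 6 and 12 months as secondary, so most of the exposure is at the secondary times. Section 3 lists all the time points for HbA1c without that ranking.

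**Simple bound, ignoring the mixed model.** Let q be the share removed in an arm and D the mean A1C of removed minus retained teens. The retained mean is the full mean minus q × D, so the TXT − EDU contrast shifts by

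bias = (q_EDU − q_TXT) × D.

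The documents give neither q nor D; both are assumed.

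- In A1C points with D = 1.0: 5% versus 2% gives (0.05 − 0.02) × 1.0 = 0.03; 10% versus 0% gives 0.10.
- In SD units with 85 per arm: SE = √(2/85) = 0.153. The difference detectable with 90% power at two-sided 0.05 is (1.960 + 1.282) × 0.153 = 0.497 SD. With a baseline correlation of 0.7 it is 0.497 × √(1 − 0.7²) = 0.355 SD.
- Type I error = Φ(−1.960 + bias/SE) + Φ(−1.960 − bias/SE).

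| Removed, TXT / EDU | Bias, D = 0.5 to 1.0 SD | Type I error, correlation 0 to 0.7 |
|---|---|---|
| 5% / 5% | 0 | 5.0% |
| 2% / 5% | 0.015 to 0.03 SD | 5.1% to 5.9% |
| 5% / 10% | 0.025 to 0.05 SD | 5.3% to 7.4% |
| 5% / 15% | 0.05 to 0.10 SD | 6.2% to 15.0% |

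Swapping the arms reverses the sign. The upper type I figures are generous: they shrink the SE for baseline but leave the bias unshrunk.

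**Plausibility of the rates.** Planned attrition is 200 × 0.15 = 30 teens. With 100 per arm, 5% / 10% means 15 removals, half of that allowance. The last row means 20, two thirds of it. Pilot retention in 5.3 was 91–98%.

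**With the mixed model of 9.3.1.** A simulation used 100 per arm, SD 1.5 (assumed), correlation 0.5 to 0.7, and 10% of EDU versus 0% of TXT removed after 3 months.

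- Removal driven by the observed 3-month A1C: the completers' bias at 12 months was 0.08 to 0.11 points; the mixed-model bias was about zero (−0.001 to −0.008).
- Removal driven by the unseen 12-month A1C: bias remained, but was 34–59% smaller than among completers.

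**Precision only.** If removals come on top of the 15%, power at 0.497 SD falls from 90% to 88.9% (164 analysed), 88.2% (160) or 86.1% (150).

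**The case against.** The strongest reply is that the rule is narrow and the analysis robust. Removal is optional and confined to a criterion that precludes further participation. A reader might infer that any teen who falls ill or joins a programme is dropped. The text does not say that: the condition must be serious and interfere with diabetes management, and the investigator must choose to act. A serious illness may also make data collection genuinely hard. This stands, but the qualifier is undefined, and neither criterion in itself prevents an A1C or a survey. Section 5.3 already offers emailed survey links, paper packets and a home A1C kit.

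The mixed model is a real defence. Where removal follows A1C already on record, it corrects nearly all of the bias. It does not do so where removal reflects deterioration not yet measured, and no missing-data sensitivity analysis is described.

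Two further inferences go too far. One is that the primary result is compromised: the synopsis puts the primary endpoint at 3 months, where exposure is smallest. The other is that this ground is distinctive because non-compliance could only ever reach TXT. Section 6.1.1 sends the affect assessment by text to all adolescents, and EDU teens also complete a behaviour contract, so the non-compliance ground can reach both arms.

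It is also fair that rewording the fourth ground alone would not be enough, because the third overlaps it.

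**Conclusion.** The point holds as a flaw in a stated rule, of modest likely size. Section 7.2 permits loss of post-randomisation outcomes for reasons related to A1C, and no other section restores them. Bias is near zero if removal is equal by arm with similar severity, or if it depends only on observed A1C. It matters when removal is both unequal by arm and tied to unobserved A1C. Under assumed rates of 5% versus 10% it is at most about 0.025 to 0.05 SD, before any mixed-model correction. Reaching 0.10 SD takes a gap of ten percentage points with removed teens a full SD worse.

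A reader might conclude that removal will differ by arm. The documents do not show this; they only leave it possible. The change is worth making because it is cheap and extends to this group an aim the protocol already states.

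**What to change.** In 7.2, separate stopping the intervention from leaving follow-up, and align the third and fourth grounds. Suggested content:

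- Exclusion criteria determine entry only.
- A randomised participant who later meets one, is found to have met one at entry, or starts an additional treatment stays in follow-up. A1C and questionnaires are collected at 3, 6 and 12 months and analysed in the assigned arm.
- The exceptions are withdrawal of consent or assent, and the existing ground that continued data collection is not in the participant's best interest.
- The event and its date are recorded in REDCap alongside the reason already required.

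Whether the intervention itself continues is a separate decision on which this point takes no position.

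The cost is a short rewording; the 200 enrolled and 170 analysed do not change. The downside is that some later values will reflect other interventions or illness. An analysis that sets values to missing after the event can be added, but only as secondary, because it relies on the missing-at-random assumption that is in doubt here.

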#### 6.1.1 Study Intervention or Experimental Manipulation Description

Participants randomized to the EDU group will complete a behavioral health contract. The health behavior contract states the behavior that they are committing to do (e.g., check blood glucose 4 times/day), when they will do it (e.g., before meals and before bedtime), and how often they will perform the target behavior (e.g., daily). They will also receive a 14-page educational packet, with age-appropriate information from the American Diabetes Association website on the following topics: understanding A1C, driving and diabetes, hyper- and hypoglycemia, and sports and exercise.

Participants randomized to the TXT group will complete a behavioral health contract. They will also receive an educational packet, with age-appropriate information from the American Diabetes Association website (e.g., understanding A1C, driving and diabetes). Adolescents in the TXT group will also complete a positive affect interview at baseline with a trained research assistant. During the positive affect interview, adolescents will be asked to list three things that make them feel good, even for just a few minutes. Next, they will be asked to choose two to three values that they personally found to be most important from the following list: Enjoying Sports, Art, Working Hard in School, Having a Sense of Humor, Being Creative, Belonging to a Social Group or Club, Following Politics or Current Events, Relationships with Friends, Relationships with Family, Faith or Spirituality, Music. The adolescents will write a few short sentences about why those values are important to them, and to provide an example of a time they accomplished something or had a good experience related to that value. Further, parents will be asked to provide positive affirmations (praise or positive messages) to their adolescents, focused on non-diabetes strengths. Parents will be given examples of messages and asked to write a sample positive message. The trained research assistant will give parents feedback on their messages to ensure that they meet the requirements.

A brief assessment of positive affect (Positive and Negative Affect Scale -- Child -- Short Form), consisting of 10 items, will be obtained from all adolescents via automated text messaging twice/month during the 8-week intervention. All adolescents will also be sent a retention item (e.g., laptop decal) halfway through the 8-week intervention period.

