#### 6.1.2 Administration and/or Dosing

Adolescents in the TXT group will receive automated text messages 5 days/week for 8 weeks. Messages will be tailored to include adolescents' responses to the baseline interview, including reminders to engage in gratitude and self-affirmation. Gratitude messages (e.g., "Last week you said [response from gratitude exercise] made you happy. Have you noticed that this week, even for a few minutes?") will be sent once/week. Important value messages (e.g., "You mentioned that [response from values exercise] was important to you, and I asked you to think about that when it was hard for you to check your blood sugar. Have you done that this week?") will be sent once/week. Mood Booster messages will be sent 2-3 times/week. Mood Boosters include inspirational messages (e.g., "Believe you can, and you're halfway there!") and humorous messages (e.g., "Which hand is it better to write with? A: Neither, it's best to write with a pen!"), based on earlier work to obtain teens' ratings of messages. Younger teens (age 13-14) will receive some different messages than older teens (age 15-17), based on ratings. Additionally, to induce positive mood, teens will be texted gift cards codes valued at \$5.00 on alternating weeks. Parents will receive weekly text message reminders to provide positive messages to their teens.

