### 9.2 SAMPLE SIZE DETERMINATION

**Power Analysis:** We plan to enroll 200 adolescent-parent dyads and conservatively assume a 15% dropout rate, leaving 170 subjects for analysis. Power calculations for the repeated-measures design were conducted using a variety of statistical simulations for each of the outcomes. Inputs into the simulation study, based on preliminary data from 46 subjects measured 3 months apart, were baseline mean, baseline standard deviation, and correlation between baseline and 3-month measurement. Table 3 summarizes the effect sizes that we will have at least 90% power to detect at a 0.05 significance level.

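### Section 7.2 allows replacement of randomised participants who do not receive the intervention, without defining receipt by arm or keeping them in follow-up and analysis

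*Combined protocol and SAP*

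**What the plan says.** Section 7.2 covers discontinuation and withdrawal from the study. It contains three relevant statements:

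- On people who never start: "Subjects who sign the informed consent form and are randomized but do not receive the study intervention may be replaced".
- On people who do start, the next sentence says that those who receive the intervention "and subsequently withdraw, or are discontinued from the study, will not be replaced".
- Among the reasons for which an investigator may discontinue a participant from the study, it lists "Significant study intervention non-compliance".

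Section 5.3 commits the team to keeping families in data collection "regardless of their engagement in the text messages so that intent-to-treat analyses may be conducted". Section 9.3.1 gives the inclusion rule: a subject is to "be included in the analysis if they have an outcome measured at baseline and at least one outcome measured at 3, 6 or 12 months". That rule sets no condition on receipt of the intervention and does not mention replacement.

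On content, Section 6.1.1 says "Participants randomized to the EDU group will complete a behavioral health contract", together with an education packet. TXT participants get the same two items plus a positive affect interview. The schedule in Section 1.3 places randomisation, contract, materials and interview at Visit 1. After that visit, TXT continues: Section 6.1.2 says "Adolescents in the TXT group will receive automated text messages 5 days/week for 8 weeks", with gift codes and weekly reminders to parents.

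**The concern.** A replacement rule that turns on what happens after randomisation needs two things: a definition of the triggering event for each arm, and a statement of what happens to the replaced person's data. Section 7.2 gives neither. Its setting suggests departure from the study, because it sits under withdrawal and is paired with a sentence about people who later withdraw.

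Receipt has no single meaning across the document. The synopsis (Section 1.1) describes the study intervention only in terms of TXT content, while Section 4.3 calls both conditions interventions. A site could therefore take receipt to mean the Visit 1 materials, the interview, or the texts. TXT offers more points at which someone could be judged not to have received it. Section 6.3 carries blinding in its title but describes none, and study personnel conduct the TXT-only interview (Section 6.2.1). A discretionary decision to replace could therefore be made with the arm known.

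If adolescents who fail to start have worse A1C or distress trajectories, and more of them leave follow-up in TXT than in EDU, the comparison tilts towards TXT. It then moves from the effect of assignment towards the effect among those who start.

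**Working it through.** **Planned numbers.** Section 9.2 states that the investigators "conservatively assume a 15% dropout rate, leaving 170 subjects for analysis". With 200 enrolled, 200 × (1 − 0.15) = 170, which reproduces the figure. That is 85 per arm under the 1:1 allocation in Section 4.1.

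**Passages side by side.**

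1. A participant is randomised, is judged not to have received the intervention, and is replaced (Section 7.2).
2. If that person is no longer followed, no outcome exists at 3, 6 or 12 months, and Section 9.3.1 excludes them. Section 5.3 aims to prevent this.
3. If that person is still followed, Section 9.3.1 includes them, and replacement only means that an extra family is enrolled.

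The text does not say whether step 2 or step 3 applies.

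**Benchmark.** The simulated effect sizes behind the 90% power claim are not in the text available, so that claim cannot be reproduced. As a benchmark only, take a two-sample comparison of 85 per arm, two-sided 0.05 (the sidedness is assumed), with no baseline adjustment:

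- SE = √(2/85) = 0.153 SD
- Detectable difference at 90% power = (1.960 + 1.282) × 0.153 = 0.497 SD

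**Bias if step 2 applies in TXT only.** Let f be the share of TXT replaced and lost to follow-up, and D the amount, in SD, by which their outcome would be worse than that of TXT starters. The full-arm mean is the starters' mean less f × D, so removal shifts TXT favourably by f × D. With no true effect, the rejection rate is 1 − Φ(1.960 − fD/SE) + Φ(−1.960 − fD/SE). Both f and D are assumptions.

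| f | D (SD) | Bias f × D (SD) | Two-sided error |
|---|---|---|---|
| 2% | 0.5 | 0.010 | 0.0505 |
| 5% | 0.5 | 0.025 | 0.053 |
| 10% | 0.5 | 0.050 | 0.062 |
| 15% | 0.8 | 0.120 | 0.12 |

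In A1C units, assuming a deficit of 0.5 to 1.0 points and f of 5% to 10%, the shift runs from 0.05 × 0.5 = 0.025 to 0.10 × 1.0 = 0.10 points. It is zero under step 3.

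**Cost of keeping non-starters.** If a share f of TXT never starts, gains nothing and is analysed, the benchmark effect becomes 0.497 × (1 − f).

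| f | Effect (SD) | Power |
|---|---|---|
| 2% | 0.487 | 88.8% |
| 5% | 0.472 | 86.9% |
| 10% | 0.448 | 83.1% |

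**The case against.** A reader might infer that the rule selectively strips non-starters from TXT and so breaks the intent-to-treat comparison. The documents do not support that reading:

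- The sentence is permissive, names no arm, and does not say that a replaced person leaves follow-up or the analysis. Read with Sections 5.3 and 9.3.1, it could mean no more than enrolling an extra family.
- TXT also begins at Visit 1 with the same contract and packet. If receipt means those items, non-start should be rare and similar in both arms, and a family that leaves straight after randomisation could belong to either.
- An adolescent who completes Visit 1 and later ignores or blocks the texts has, on a natural reading, received intervention. The next sentence of Section 7.2 then rules out replacement.

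All of this stands. So does a further objection: the bias comes from lost follow-up, not from the substitute. Someone with no post-baseline outcome is out of the analysis whether or not they are replaced, so deleting the sentence would not be enough without a follow-up commitment.

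These arguments do not settle what receipt means, nor do they state that replaced participants are followed. The benign reading has to be assembled from three sections, and the most natural reading of Section 7.2 alone is departure from the study. The non-compliance ground in the same section reinforces that reading and sits badly with Section 5.3.

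**Conclusion.** The concern holds as a gap in the plan and an avoidable risk of selection after randomisation. It is not a demonstrated bias. Section 7.2 leaves receipt undefined by arm and the follow-up and analysis status of replaced participants unstated. If they are not followed, the section conflicts with the aim in Section 5.3.

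Uneven use between the arms is possible because TXT has more components and the staff delivering them know the arm, but the documents do not show that it would occur. The size depends on two quantities they do not give: how many people fail to start, and how different their outcomes would be. With 2% to 10% of TXT removed, none removed from EDU, and a 0.5 SD deficit, the two-sided error stays between 0.0505 and 0.062. Only a more extreme pair of assumptions (15% and 0.8 SD) takes it to about 0.12. It is worth correcting because the remedy is cheap and sound under either reading.

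**What to change.** Amend Section 7.2 as follows.

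- Delete the replacement sentence. State that every randomised participant, whether or not the assigned intervention was received, counts toward the 200, is followed for A1C and surveys at 3, 6 and 12 months unless consent is withdrawn, and is analysed in the assigned arm.
- State that any additional family takes the next allocation on the randomisation list, within its device-use stratum.
- Define receipt for TXT and for EDU, for descriptive reporting only.
- Reconcile the non-compliance ground for study discontinuation with Section 5.3, so that non-compliance with the intervention does not end data collection.
- If any replacement has already taken place, report the numbers by arm.

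The planned 200 randomised and 170 analysed do not change. The cost is a short amendment and some dilution from untreated participants who stay in the analysis. The 15% allowance in Section 9.2 does not cover that dilution, because it allows for people missing from the analysis, not for people analysed but untreated. On the benchmark, 5% non-start in TXT with no gain takes power from 90% to about 87%.
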